3.3 Data Source

The proposed study will utilize data from the IMS Brogan's Longitudinal Patient Data assets (LRx). LRx tracks the prescription activity of anonymized patients over time (longitudinally), with records dating back to 2004. Collection of prescriptions that include anonymized patient data from approximately 4,000 pharmacies nationwide enables visibility to all payer types and is ideally suited to provide insights into chronic, retail-based markets. LRx data is un-projected and is based on a large sample (~75% coverage nationally, see table 1). By tracking patient prescription history, LRx goes beyond measuring prescription volumes to tracking real-world behaviour and use.

Table 2: Coverage of LifeLink (LRx) Patient Longitudinal Database

Region	% Coverage
	As a % of projected Rx volume in CompuScript – MAT Dec 2011
Total Canada	74.6%
British Columbia	66.4%
Alberta	68.8%

Saskatchewan	71.9%
Manitoba	79.6%
Ontario	75.8%
Quebec	76.7%
New Brunswick	95.7%
Nova Scotia	67.2%
Newfoundland / PEI	53.1%

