3.4.3 Study Population

Inclusion/Exclusion Criteria:

All patients in the LRx database who have been prescribed Byetta in Canada during the analysis period will be included in the study. Patients with inconsistent records and/or insufficient data, as shown in table 3, will be omitted to restrict the analysis to a consistent and robust patient sample.

Exclusion criteria are required since the pharmacy data (LRx) is driven through data entry at the individual stores. The criteria are used to filter out transactions that either have entry mistakes or have place-holder information that is not accurate. The exclusion criteria are established to ensure a consistent record for patients in the study sample. Inclusion and exclusion criteria may be modified during the initial stages of the project.

Table 3: Exclusion criteria applied to remove patients with inconsistent Rx history

Criteria	Conditions for Exclusion	Rationale
Demographic Criteria	Patients without a consistent year of birth, province, or gender	Patients without a consistent demographic record of gender, year of birth and province are not reliable due to inconsistencies
Constant Store Criteria	Patients at stores with inconsistent reporting after May 2011	Stores with inconsistent recorded information will not have accurate information on what prescriptions a patient received
Max Rx Criteria	Patients with more than 208 Rx/year	This is to eliminate pharmacist error
Min Rx Criteria	Patients with fewer than 6 Rx	Patient with less than 6 prescriptions are excluded because there is the potential for including the same patient multiple times as occasionally patients fill prescriptions at different pharmacies when traveling or for convenience
Consistent Patients	Remove patients without any prior Rx at a store	Removing patients without any other prior prescriptions at a store also eliminates patients who have changed pharmacies and may be included multiple times in the data
Analysis Period	Remove patients without any	Patients who do not have a prescription

	Rx in the Analysis Period	in the analysis period cannot be included as they do not have any prescriptions to analyze
12 Month Gap	Remove patients with a year gap between Diabetes Rx	Patients with a year gap between diabetes prescriptions are likely to have filled prescriptions at an alternative pharmacy and could be counted multiple times in the data set

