3.4.4 Study Outcomes and Definitions

[figure not shown]
The primary outcome of interest is the off label use of Byetta in Canada.

A patient's therapy type will be inferred by identifying if a patient switches between, or adds on to therapies, as shown in figure 3.

Mono Therapy is defined as a patient receiving a specific therapy (Therapy 1) prior to a different therapy (Therapy 2) where Therapy 1 is not detected after Therapy 2 initiation. Mono therapy for this study, refers to a patient received a prescription for only one product at a given time.

Concomitant Therapy is defined as a patient receiving a specific therapy (Therapy 1) prior to a different therapy (Therapy 2) where Therapy 1 is detected after Therapy 2 initiation.

Figure 3: Distinguishing between add-on and switch therapies

Patients will be selected for the study if they receive a Byetta script anytime during the analysis period and if they met the inclusion criteria. To identify on-label vs. off-label use, patient history will then be used to classify patients as "inferred on-label" if they also received Metformin and/or SU or Lantus during the study (Business rules 1 and 2 in Table 5).

All other patients that do not meet the criteria for use of Byetta with metformin and/or SU or Lantus will be classified as “inferred off-label”. The group of patients classified as “inferred off-label” will then be further classified to gain a better understanding of the trends in “inferred off-label” use of Byetta (Business rules 3-10 in Table 5).

The Business rules described in Table 5 are prioritized to ensure the appropriate classification of each patient. Therefore patients will be classified based on the highest rank business rule. For example, if a patient receives scripts for both Metformin and other insulin during the analysis period, they will be classified as “inferred on-label” as they have a script for metformin and therefore are classified by business rules 1 and 2

Note: The patient classification categories (‘Inferred Adherence Label’) can be modified in the initial phase of the project.

Table 5: Business rules applied to classify patients as “on-label” vs. “off-label”

(The business rules have been structured to align with the Canada monograph for Byetta indication and clinical use (see Table 1) and will be finalized upon study initiation).

Rank	Business Rules	Cohort Description	Inferred Adherence Label

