1	Concomitant use of* Byetta with metformin (met) and/or sulfonylurea (SU), OR Concomitant use of Byetta with Lantus	Met and/or SU or Lantus is prescribed with Byetta	Inferred On-label
2	Evidence of** Byetta and metformin and/or sulfonylurea OR Evidence of Byetta and Lantus	Met and/or SU or Lantus is not prescribed with Byetta, but both appear in the analysis period	Inferred On-label
3	Evidence of Byetta and Levemir	Levemir is prescribed in the analysis period	Off-Label Insulin Use
4	Evidence of Byetta and Human Basal Insulin	Human basal insulin is prescribed in the analysis period	
5	Evidence of Byetta and thiazolidinedione (TZD)	TZD is prescribed in the analysis period	Off-Label OAD Use

6	Byetta Alone	No other products prescribed in the analysis period	Inferred Off-label
7	Evidence of Byetta and all other insulin	Other insulin is prescribed in the analysis period	
8	Evidence of Byetta and all other OADs	Other OADs are prescribed in the analysis period	
9	Pediatric Patients	Patient is under the age of 18 (<18)	
10	All other combinations	All other combinations	

Note: Evidence of Diabetic ketoacidosis, diabetic coma/precoma and end stage renal disease cannot be inferred from the dataset; therefore we will not be able to identify these patients as a separate group

* "Concomitant use of..." refers to continued use of Byetta and other product

** "Evidence of..." refers to anytime within the study period including look-back or look forward periods

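### Rank 6 (Byetta Alone) counts a patient as off-label when partner drugs may simply have been filled at another pharmacy, which biases the primary outcome upward, and Table 6 cannot show by how much

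*Protocol*

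**What the plan says.** Section 3.4.4 makes off-label the default. The text reads "All other patients that do not meet the criteria for use of Byetta with metformin and/or SU or Lantus will be classified as" inferred off-label. Within that group, rank 6 of Table 5 is Byetta Alone, described as "No other products prescribed in the analysis period". Ranks 1 and 2 are applied first and make a patient on-label on recorded metformin, SU or Lantus. The footnote to Table 5 says that evidence of a product "refers to anytime within the study period including look-back or look forward periods".

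Table 3 in section 3.4.3 describes the records on which this rests. The minimum-prescription filter is justified by the "potential for including the same patient multiple times as occasionally patients fill prescriptions at different pharmacies when traveling or for convenience". The filter on prior prescriptions at a store "eliminates patients who have changed pharmacies and may be included multiple times in the data". The 12-month-gap filter removes patients who are "likely to have filled prescriptions at an alternative pharmacy and could be counted multiple times in the data set". Section 3.3 gives national coverage of about 75% of prescription volume.

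Section 3.4.7 calls the labels an estimation and says that off-label use is probably over-estimated. The reason it gives is that the on-label rules are stringent and everyone else defaults to off-label. Table 6 in section 3.4.6 has four rows (on-label, off-label insulin, off-label OAD, off-label) and none for Byetta Alone.

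**The concern.** To infer monotherapy from the absence of other products, the dispensing record has to be complete for that patient's diabetes drugs. Table 3 says that one person may appear several times after using different pharmacies. That can happen only if such fills are not joined into one record. Absence from the record then has two explanations, which rank 6 does not separate: the patient took no partner drug, or filled it somewhere else.

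For a truly on-label patient, unseen metformin, SU or Lantus fills can only move the label from on to off. The error goes straight into the primary outcome, in a study done to answer a Health Canada request about use outside the label. Because Table 6 appears to pool Byetta Alone with the other residual groups, a reader could neither see the affected patients nor take them out.

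**Working it through.** **Step 1. Does a split-pharmacy patient pass the filters?** Take a patient who fills Byetta and unrelated drugs at store A, and metformin at store B.

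| Table 3 filter | Requirement | Store A record |
|---|---|---|
| Minimum Rx | at least 6, of any kind | can pass |
| Prior Rx at the store | any drug | can pass |
| 12-month gap | no year-long gap in diabetes Rx; Byetta is itself a diabetes product in Table 4 | passes with regular Byetta fills |
| Look-back and follow-up | 6 months before, 3 months after | can pass |
| Constant store | consistent reporting by the store | says nothing about store B |

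No filter requires a diabetes drug other than Byetta at store A. The store A record is classified off-label. The store B record holds no Byetta and is never selected.

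**Step 2. Which rank?** If no other diabetes product is visible, rank 6. If rank 6 is read as excluding any product at all, the unrelated drugs send the patient to rank 10, which is still off-label by default. If a different diabetes product is visible (Levemir, a TZD, another insulin, another OAD), the patient falls in rank 3, 4, 5, 7 or 8, also off-label.

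**Step 3. Size of the bias.** The protocol states no expected off-label share and no split-pharmacy rate, so it has no figure to reproduce. Let p be the true off-label share and m the share of truly on-label patients whose metformin, SU and Lantus fills are all missing from the record. Both are assumed.

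Observed off-label share = p + (1 − p)m

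Misclassified part of those labelled off-label = (1 − p)m / [p + (1 − p)m]

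For example, with p = 20% and m = 5%: 0.20 + 0.80 × 0.05 = 0.24, and 0.04 / 0.24 = 17%.

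| True p | m = 2% | m = 5% | m = 10% |
|---|---|---|---|
| 10% | 11.8% (15% misclassified) | 14.5% (31%) | 19.0% (47%) |
| 20% | 21.6% (7%) | 24.0% (17%) | 28.0% (29%) |
| 30% | 31.4% (4%) | 33.5% (10%) | 37.0% (19%) |

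**Step 4. What reporting two totals would show.** Assume p = 20%, of which true monotherapy is 5 points, with m = 5% and every missed patient landing in rank 6. Rank 6 then holds 5% + 4% = 9% of patients. Off-label use is 24% with rank 6 counted. With rank 6 set aside it is 24% − 9% = 15% of all patients, or 15 / 91 = 16.5% of those remaining. Neither equals the true 20%, but the distance between the totals shows how much of the result rests on rank 6.

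**The case against.** The protocol does not claim proof. It calls the labels inferred, and section 3.4.7 already admits bias in this direction, pointing to the same default rule. This stands as far as it goes, but stringent rules and incomplete capture are different causes, and only the first is named.

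The affected group is narrow. On the Table 5 footnote, a single visible metformin, SU or Lantus fill at any time in the study period, look-back and follow-up included, makes the patient on-label. Only patients with every such fill elsewhere are misclassified. This also stands. Some filters, such as constant store reporting and look-back, do concern the consistency of the record and not only double counting. They reduce the problem without removing it.

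Three stronger readings are tempting, and the protocol does not support them:

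- The roughly 25% of volume outside the panel might be taken as the rate of missed partner fills. It is a share of prescription volume. Patients wholly outside the panel are not in the study, and the figure does not say how often one patient divides fills between stores.
- A reader might infer that Byetta Alone is mostly artefact. With p = 20% and an assumed 5% true monotherapy, the false share of rank 6 is 0.016/0.066 = 24%, 0.04/0.09 = 44% and 0.08/0.13 = 62% for m = 2%, 5% and 10%. It passes one half only when 0.80m exceeds 5%, that is m above 6.25%. These figures also assume that no missed patient has another visible diabetes product.
- Repeated non-diabetes fills at the same store might seem to confirm monotherapy. They do not: if the unrelated drugs are chronic, the store A patient above has such fills and still takes metformin.

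Finally, the categories may be modified at study start, and sensitivity analyses are often left to an analysis plan, which is not at hand. That limits the weight of the point. The classification rule, the Table 6 layout and the explanation in 3.4.7 are nevertheless all set out in the protocol.

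**Conclusion.** The concern holds in a limited form. Following Table 5 as written counts as off-label any truly on-label patient whose metformin, SU and Lantus fills are all made at another pharmacy, and this pushes the primary outcome upward. The protocol does not allow the amount to be estimated; across the assumed values in the working, the inflation runs from 1.4 points (p = 30%, m = 2%) to 9 points (p = 10%, m = 10%).

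The conclusion rests on two readings. One is that records are not joined across stores, which is inferred from the rationales in Table 3 and not stated outright. The other is that the off-label row of Table 6 pools rank 6 with ranks 7 to 10, as the labels in Table 5 suggest.

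**What to change.** 1. Add a separate Byetta Alone row to Table 6.
2. Report total off-label use twice: once with rank 6 counted as off-label, and once with rank 6 set aside as not classifiable. State the denominator of the second figure.
3. In section 3.4.7, name partner drugs filled at another pharmacy as a further source of over-estimation, distinct from stringent rules.

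A split of rank 6 by repeated non-diabetes fills at the same store could be added only as an exploratory proxy, since it does not show that partner drugs were not filled elsewhere. It also needs drug-level data on non-diabetes products, which Table 4 does not list as tracked.

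The three main changes use patients already classified and need no new extraction, and section 3.4.4 leaves the categories open to change. The cost is two figures in place of one. The second also sets aside true monotherapy, and missed patients in other off-label ranks remain in it, so it should be presented as a sensitivity figure and not as a corrected estimate.

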3.1 Rationale

Exenatide is an injectable glucagon-like peptide 1 (GLP-1) receptor agonist approved as an adjunct to diet and exercise to improve glycemic control in adults with type 2 diabetes mellitus (T2DM) by the United States and Europe. Byetta (exenatide twice daily) is administered as a subcutaneous injection within 1 hour before the two main meals of the day, approximately 6 hours or more apart. Treatment is typically initiated at 5 mcg per dose, twice daily, and may be increased to 10 mcg twice daily based on the patient’s clinical response.

During Health Canada’s review of the marketing authorisation application of exenatide, Lilly provided a commitment to monitor the off-label use and compliance to the Summary of Product Characteristics (SPC) of exenatide prescriptions through a post-launch utilization study. Specifically, Health Canada requested that:

The RMP should be revised to include a post-marketing study conducted on exenatide use and adherence to labeling recommendations in Canada, similar to the drug utilization study requested by the EU Regulatory authority that is currently ongoing in various EU countries. Since preliminary information has already indicated off label use of exenatide with either TZD or insulin in the EU, the need for further study and/or additional risk management actions with these products should be specifically addressed.

Table 1: Canadian Byetta Indication

Byetta Monograph
Indication and Clinical Use:
BYETTA is indicated in combination with metformin and/or sulfonylurea to improve glycemic control in patients with type 2 diabetes mellitus, when maximally tolerated doses of these oral therapies in addition to diet and exercise do not provide adequate glycemic control.
BYETTA is indicated in combination with insulin glargine (with or without metformin) to improve glycemic control in patients with type 2 diabetes mellitus when insulin glargine (with or without metformin) in addition to diet and exercise, does not provide adequate glycemic control
Contraindication:
BYETTA should not be used in the pediatric patient population.

BYETTA should not be used in patients with end-stage renal disease or severe renal impairment (creatinine clearance <30 mL/min), including patients receiving dialysis

BYETTA is contraindicated in patients with diabetic ketoacidosis, diabetic coma/precoma or type 1 diabetes mellitus.

Source: Byetta Drug Product Monograph, Canadian Pharmacists Association, online version, April 2011.

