3.2.2 Secondary Objective

To assess the concomitant use of exenatide with either thiazolidinediones (TZDs) or insulin.

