3.4.6 Analysis Plan

The data extracted will be analyzed to complete the following 3 tables requested for each study year. The results will be provided as percent of patients who are "inferred on-label" and patients who are "inferred off-label", stratified by gender. Any off-label use in the pediatric population will be described (by gender and concomitant use). Results for the first report (year 1 and year 2 data) will be available in Q4 of 2013 and results for year 3 data will be available in Q4 of 2014.

Table 6: Indications for patients prescribed Byetta**(Patients over the age of 18)**

Indication	Male		Female	
	# of Patients	% of Patients	# of Patients	% of Patients
Inferred On-Label				
Off-Label Insulin Use				
Off-Label OAD Use				
Off-Label				

Table 7: Byetta Concomitant medications

Concomitant medications	All Patients (>17 yrs) N (%)	Inferred On-Label N (%)	Inferred off-label (all combinations) N (%)	Off-Label Insulin Use N (%)	Off-Label OAD Use N (%)	Off-Label N (%)
Oral anti-glycaemics						
Metformin						
SU						
TZD						
Others						
Insulin						

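### Table 6's off-label insulin and OAD rows do not measure off-label insulin or TZD co-use, and Table 7's single insulin row repairs this only in part

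*Protocol*

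**What the plan says.** The secondary objective (Protocol 3.2.2) is "To assess the concomitant use of exenatide with either thiazolidinediones (TZDs) or insulin". The Rationale (3.1) gives its origin. The regulator asked for the study because "preliminary information has already indicated off label use of exenatide with either TZD or insulin in the EU". Table 1 in the same section names one labelled insulin: "BYETTA is indicated in combination with insulin glargine (with or without metformin) to improve glycemic control".

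Section 3.4.4 separates adding on from switching. Therapy is concomitant "where Therapy 1 is detected after Therapy 2 initiation"; if the first therapy is not seen again, the patient has switched.

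Table 5 then gives each patient one label, and the highest applicable rank wins:

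- Ranks 1 and 2 (metformin, SU or Lantus) are on-label. Only rank 1 asks for concomitant use.
- Rank 3, "Evidence of Byetta and Levemir", carries the off-label insulin label. Rank 4 (human basal insulin) has a blank label cell below it.
- Rank 5 (TZD) carries the off-label OAD label.
- Rank 6 (Byetta alone) carries the general off-label label. Rank 7, "Evidence of Byetta and all other insulin", has a blank label cell below it.

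Table 6 (3.4.6) has one row per label, including "Off-Label Insulin Use". Table 7 lists concomitant medications, with a TZD row and one insulin row, in columns for all adult patients, on-label patients and four off-label groupings.

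**The concern.** A reader will take the Table 6 row named for off-label insulin as the number of patients using Byetta with an unlabelled insulin, and the OAD row as the corresponding TZD number. Neither row is built that way. Some unlabelled insulins are filed elsewhere, a patient with both insulin and a TZD appears in one row only, and past use counts the same as concurrent use. These faults pull in different directions: misfiling lowers a row, while counting past users raises it. The net error therefore cannot be signed in advance. At stake is the regulator's specific question on TZD and insulin, which the study was set up to answer.

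**Working it through.** The plan gives no figure on this point, so there is none to reproduce. The check is to run drug combinations through Table 5 and see where each lands.

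**Inputs.** Ranks and labels come from Table 5, product groups from Table 4, output rows from Tables 6 and 7. Blank label cells are read as merged with the label above. The paediatric rule and Victoza are left out.

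**Rule applied.** Any metformin, SU or Lantus: on-label. Otherwise any Levemir or human basal: insulin row. Otherwise any TZD: OAD row. Otherwise: residual row.

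**Count with eight classes** (metformin, SU, Lantus, Levemir, human basal, premix and rapid pooled, TZD, other OAD):

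- Non-glargine insulin present: (2^3 − 1) × 2^5 = 7 × 32 = 224.
- Of these on-label: 7 × (2^3 − 1) × 2^2 = 7 × 7 × 4 = 196. Left: 224 − 196 = 28.
- Of the 28, Levemir or human basal present: 6 × 4 = 24. Premix/rapid only: 1 × 4 = 4, of which 2 have a TZD (OAD row) and 2 do not (residual).
- TZD present: 2^7 = 128. On-label: 7 × 2^4 = 112. Left: 16, of which 3 × 4 = 12 go to the insulin row and 4 to the OAD row.

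With premix and rapid as separate classes (nine classes, 512 patterns) the picture is the same:

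| Patterns containing | Classes | Total | On-label | Insulin row | OAD row | Residual |
|---|---|---|---|---|---|---|
| Non-glargine insulin | 8 | 224 | 196 | 24 | 2 | 2 |
| Non-glargine insulin | 9 | 480 | 420 | 48 | 6 | 6 |
| TZD | 8 | 128 | 112 | 12 | 4 | 0 |
| TZD | 9 | 256 | 224 | 24 | 8 | 0 |
| Premix/rapid the only insulin, no metformin or SU | 9 | 12 | 0 | 0 | 6 | 6 |

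The last line isolates the labelling fault: none of those 12 patterns reaches the insulin row. Premix and rapid make up 4 of the 6 insulin groups in Table 4. Setting the on-label override aside, the insulin row misses 4 of 28 patterns (eight classes) or 12 of 60 (nine classes, 480 − 420 = 60). The OAD row holds 4 of 16 TZD patterns, or 8 of 32 (256 − 224 = 32).

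**Timing.** Take a patient with no metformin, SU or Lantus whose TZD ended before Byetta began. Section 3.4.4 calls this a switch. The Table 5 footnote lets evidence come from any part of the study period, look-back included, so rank 5 applies and the patient enters the OAD row. The rank 5 cohort description places the TZD in the analysis period. That conflicts with the footnote if the last TZD script fell in the look-back, but it still admits a script inside the analysis period and before the first Byetta. Neither text requires a TZD script after Byetta starts. The same holds for ranks 3, 4 and 7.

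**Table 7, cell by cell.**

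- TZD row, all-patients column: independent of the Table 5 label, so the hierarchy does no harm here.
- Insulin row, off-label columns: no Lantus, because all 256 Lantus patterns in the nine-class count are on-label. The residual column recovers rank 7, and the OAD column recovers TZD plus premix or rapid.
- Insulin row, on-label and all-patients columns: Lantus is pooled with metformin or SU plus any other insulin, which the worked example in 3.4.4 places on-label.
- Definition of use: the title speaks of concomitant medications, but 3.4.6 does not say which of the two definitions applies.

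**The case against.** The best defence is that Table 6 serves the primary outcome and Table 7 the secondary one. Ranks 3 to 10 only sub-classify patients already called off-label, and Table 7 is not hierarchical. Its TZD row over all patients gives the TZD half, its off-label columns give non-Lantus insulin, and the objective says only insulin, so even a pooled row meets its wording. The labels of ranks 4 and 7 are read from blank cells. Section 3.4.6 announces three tables and two are visible, and 3.4.4 allows the rules to be modified and finalized at study start.

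Much of this stands. A reader might infer that the plan cannot answer the secondary objective, or that no planned table recovers the missing counts. The documents do not support either statement, for the reasons just given. A reader might also turn 24 of 224 into a share of patients missed. That is not supported: patterns are not weighted by how often they occur, the totals depend on how classes are split, and most of the diversion is the stated on-label rule. Nor do premix and rapid insulins always go to the residual row; they do so only without metformin, SU, Lantus, Levemir, human basal insulin or a TZD.

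Three things are not answered. The Table 6 rows still carry names they do not fit. The off-label TZD and insulin rules still ignore the add-on/switch distinction that 3.4.4 draws, and for which 3.4.2 and Table 3 require three months of follow-up. And non-glargine insulin among on-label patients remains inseparable from Lantus in the visible tables. The label and the evidence rule are set in the protocol itself, so a separate analysis plan would not excuse them.

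**Conclusion.** Wrong as written, in a limited form. The two Table 6 rows do not measure off-label insulin or TZD co-use: one omits patients whose only insulin is premix or rapid, and both admit patients who stopped the drug before Byetta. Table 7 repairs the hierarchy for TZD over all patients and for insulin in the off-label columns. It does not do so for insulin in the on-label and all-patients columns, and its definition of use is open.

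The effect in patients cannot be computed, since the protocol gives no regimen frequencies. The conclusion on rank 7 assumes that blank label cells are merged with the cell above. The conclusion on Table 7 assumes that the third announced table holds no insulin breakdown. The timing point depends on neither assumption.

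**What to change.** - In Table 5, label rank 7 as off-label insulin use. In the counts above, this raises the insulin row from 24 to 26 of 28 patterns not overridden (48 to 54 of 60). TZD plus premix or rapid stays in the OAD row, so relabelling alone is not enough.
- Build the Table 7 TZD and insulin rows on the section 3.4.4 concomitant definition, for all adult Byetta patients whatever their Table 5 label, and state this in 3.4.6.
- Split the Table 7 insulin row into Lantus, Levemir, human basal, premix and rapid.
- Reconcile the Table 5 footnote with the cohort descriptions on the time window.

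The cost is a few more rows from data already extracted, since Table 4 tracks every product. The rows overlap and will not add to 100%, which a footnote can say. As section 3.4.4 leaves the rules to be finalized at study initiation, the change fits there.

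### Table 5 has no age condition at ranks 1-2, so a child on Byetta with metformin, a sulfonylurea or Lantus is classed on-label although the label excludes paediatric use

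*Protocol*

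**What the plan says.** The label position is in Table 1 (section 3.1), under contraindications: "BYETTA should not be used in the pediatric patient population". Section 3.4.4 states that Table 5 was built to align with that monograph.

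Table 5 has ten ranked rules. Ranks 1 and 2 give the inferred on-label class to any Byetta patient with metformin, a sulfonylurea or Lantus, either used together with Byetta or appearing in the patient's study record. Neither rule mentions age. Rank 9 is the paediatric rule: "Patient is under the age of 18 (<18").

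On precedence, section 3.4.4 says "patients will be classified based on the highest rank business rule". Its worked example is a patient with both metformin and another insulin: "they will be classified as “inferred on-label” as they have a script for metformin and therefore are classified by business rules 1 and 2". The same section uses rules 3-10 only to subdivide patients who have already failed rules 1-2.

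On reporting, section 3.4.6 says "Any off-label use in the pediatric population will be described (by gender and concomitant use"). Table 6 is headed "Patients over the age of 18", and the first column of Table 7 is "All Patients (>17 yrs").

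**The concern.** The label excludes children whatever else they take, so every user under 18 is off-label. A hierarchy that asks about co-medication before age can give a child the opposite class. Off-label use is the primary outcome, and the study answers a regulator's request about adherence to labelling. The protocol says that ketoacidosis, coma or precoma and end-stage renal disease cannot be inferred from the data. Age, by contrast, can be judged from a recorded demographic field, since Table 3 requires a consistent year of birth. It is one of the few label exclusions that the study can check directly, and a prescription for metformin should not override it.

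What is at stake is the paediatric description in section 3.4.6. If it follows the Table 5 classes, a child classed on-label falls outside it, and the adult tables do not count that child either.

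**Working it through.** The plan gives no figure to reproduce. The check is to apply Table 5 as written to a patient under 18.

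**Inputs**
- Table 1: paediatric use is excluded, with no exception for co-medication.
- Section 3.4.3 and Table 3: no inclusion or exclusion criterion refers to age under 18, so children enter the study population.
- Section 3.4.4: the highest-ranked rule met decides, and rules 3-10 apply only after rules 1-2 have failed.
- Tables 4 and 5: the co-medication the rules act on can be reduced to nine classes, namely metformin, sulfonylurea, Lantus, Levemir, human basal insulin, TZD, other insulin, other OAD and Victoza.

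**One case.** A child on Byetta plus metformin meets rank 1 or 2 and is classed inferred on-label. Rank 9 is never consulted. The worked example in section 3.4.4 has the same form, with a lower-ranked off-label rule overridden by the metformin script.

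**All combinations.** Each of the nine classes is present or absent, giving 2^9 = 512 combinations for a child.

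| Rank reached | Condition | Combinations |
|---|---|---|
| 1-2 | any of metformin, SU, Lantus | 512 − 2^6 = 448 |
| 3 | Levemir | 2^5 = 32 |
| 4 | human basal insulin | 2^4 = 16 |
| 5 | TZD | 2^3 = 8 |
| 6 | Byetta alone | 1 |
| 7 | other insulin | 2^2 = 4 |
| 8 | other OAD, no insulin | 2 |
| 9 | Victoza as the only other product | 1 |

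Ranks 3-8 total 32 + 16 + 8 + 1 + 4 + 2 = 63, and 448 + 63 + 1 = 512. These are counts of possible drug combinations. They are not expected shares of patients.

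**With age tested first.** All 512 combinations are classed paediatric and off-label, and none is on-label.

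**Reporting.** Children at ranks 3-9 have failed rules 1-2, so they are off-label and fall within the section 3.4.6 description. Children at ranks 1-2 are nominally on-label. Read literally, they are outside that description, and they are outside Tables 6 and 7 by age.

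**Age cuts, in whole years.** Rank 9 covers ages up to 17 and Table 7 covers 18 and above, so these two agree. Table 6, read literally, starts at 19. A patient aged exactly 18 is counted in Table 7 but is in neither Table 6 nor the paediatric group.

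**The case against.** The strongest reply is that the protocol already treats children separately. Section 3.4.6 takes them out of the tables and promises a description by gender and concomitant use. Since Table 1 excludes all paediatric use, off-label use in children could be read as all use in children, and a breakdown by concomitant use would have little content if it covered only rank 9. That reading is reasonable and may be what was intended. It conflicts with the stated precedence, however, and the protocol does not say which governs. The loss of these children from the report is therefore possible, not certain.

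A second reply is that section 3.4.4 calls the rules provisional, to be finalised when the study starts. This leaves room for a correction but does not make one.

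Two stronger readings are tempting, and the documents support neither:
- Because rank 9 is almost unreachable, a reader might infer that paediatric off-label use would be reported as close to zero. Rank 9 does not decide off-label status. Failing rules 1-2 does, so children at ranks 3-8 remain off-label and within the planned description.
- A reader might take the 448 of 512 combinations, or the near-empty rank 9, to mean that nearly all children are misclassified. The share of children on metformin, a sulfonylurea or Lantus is not given and cannot be derived from counts of combinations.

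Nor does the ranking bias the main results. Tables 6 and 7 exclude children, so the adult on-label and off-label percentages are the same under either ordering.

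**Conclusion.** The point holds in a limited form. As written, Table 5 classes a patient under 18 with metformin, a sulfonylurea or Lantus as on-label, which contradicts Table 1 and the stated aim of aligning with it. Those children could be left out of all reported results. Other children keep the correct off-label status and lose only the paediatric sub-label. That sub-label is reached only when Victoza is the sole other tracked product.

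The number of children affected is unknown. It is probably small, which is a judgement and not a figure from the protocol. The conclusion assumes that rank 1 is the highest rank, as the worked example shows, and that section 3.4.6 uses off-label in the Table 5 sense.

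The mismatch in age cuts is a separate, minor slip. It touches only patients aged exactly 18 and gives Tables 6 and 7 different denominators if any such patients exist. This should be corrected before the rules are finalised, but it does not threaten the adult findings.

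**What to change.** 1. In Table 5, test age under 18 before ranks 1-2 and class it off-label regardless of co-medication. Alternatively, state that Table 5 applies to adults only and that all use under 18 is off-label.
2. In section 3.4.6, describe all paediatric Byetta users by gender and concomitant use, so that inclusion does not depend on the Table 5 class.
3. In section 3.4.4, adjust the text that refers to rules 1-2 and rules 3-10 so that it matches the new order.
4. Head Table 6 as age 18 and over, to agree with Table 7 and with the under-18 cut in the paediatric rule.

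The cost is one re-ordered rule, one table heading and a few sentences in two sections. No additional data are needed and no adult percentage changes because of the re-ordering. Table 6 counts change only if there are patients aged exactly 18.
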